GlaxoSmithKline

CONFIDENTIAL

CONFIDENTIAL

HEALTH OUTCOMES STUDY PROTOCOL

UNIQUE IDENTIFIER	HO-18-18992 ETrack: 208782
FULL TITLE	Claims-linked Survey Study to Assess Burden of Illness among Patients Treated with LAMA/LABA vs ICS/LABA Single Inhaler Dual Therapy
ABBREVIATED TITLE	COPD Dual Therapy Burden of Illness
FINAL PROTOCOL APPROVED	17-4-2018
SPONSORSHIP	Sponsored
DIVISION	Pharma
BUSINESS UNIT	US Medical Affairs
DEPARTMENT	USHO
STUDY ACCOUNTABLE PERSON	PPD ScD, Director, CEVEO
CONTRIBUTING AUTHORS	PPD PhD, Director, CEVEO PPD PharmD, Senior Director, CEVEO PPD MA, Associate Director, Optum

ASSET ID	17379
GSK ASSET	Fluticasone/Salmeterol 250/50 mcg (Advair) Umeclidinium/Vilanterol 62.5/25 mcg (Anoro)
INDICATION	COPD

SPONSOR SIGNATORY

PPD

[name]

VP Customer Engagement Values Evidence and Outcomes,
Medical Affairs NA

4/18-2018

Date

PROTOCOL SYNOPSIS

Unique Identifier	HO-18-18992
Abbreviated Title	COPD Dual Therapy Burden of Illness
GSK Product	Fluticasone/Salmeterol 250/50 mcg (FLUT/SAL; Advair) Umeclidinium/Vilanterol 62.5/25 mcg (UMEC/VI; Anoro)
Rationale	The purpose of the study is to assess COPD burden of illness using both patient-reported symptom burden and claims-based economic burden among patients treated with FLUT/SAL or UMEC/VI to support GOLD category B recommendations.
Objectives (Primary, Secondary)	
Primary Objective
 
 The primary objective is to compare patient-reported COPD symptom burden among patients treated with umeclidinium/vilanterol (UMEC/VI) or fluticasone/salmeterol (FLUT/SAL) 
Secondary Objectives
 
 Describe baseline all-cause, COPD-related, and exacerbation-related health care resource utilization, costs, and clinical characteristics (e.g., comorbidities, treatment history) in patients treated with UMEC/VI or FLUT/SAL Identify the GOLD classification of patients treated with FLUT/SAL or UMEC/VI.
Study Design	This is a claims-linked cross-sectional observational survey study of Medicare Advantage (MA) enrollees of a large US health plan with evidence of COPD and single-inhaler dual therapy treatments FLUT/SAL or UMEC/VI. Patients will be recruited using Optum's health plan recruitment strategy. For this approach, patients will be identified in the Optum Research Database (ORD) following receipt of the appropriate approvals. Patients will complete a mailed cross-sectional survey to collect information on patients' condition history, current treatment, smoking history, symptoms and symptom severity (mMRC and CAT), and demographic and sociodemographic characteristics. Patient survey and diary responses are linked to medical and pharmacy claims for the 12-month period prior to the survey (baseline). A 30-35% response rate is estimated based on previous patient survey studies. Two waves of data collection are anticipated to meet the target sample size based on patient counts and estimated response rate. Descriptive and multivariable techniques are used for analysis.
Study Population and Sampling Methods	
Inclusion Criteria:
 
 ≥2 ICD-10-CM diagnosis codes for COPD at least 30 days apart during the 12 month period prior to sample identification 
 Diagnosis codes J40-J44 will be included ≥1 pharmacy claim for UMEC/VI or FLUT/SAL single-inhaler dual therapy during baseline Age ≥ 65 Self-reported health care provider diagnosis of COPD Self-reported prescription for FLUT/SAL or UMEC/VI 12 months of continuous enrollment during the baseline period Ability to complete the study survey in English 
Exclusion criteria:

	
 12 month period prior to sample identification Claims for both UMEC/VI and FLUT/SAL in the 6 months closest to sample identification Claims for triple therapy (ICS + LAMA + LABA) during the baseline period Evidence of lung cancer diagnosis and/or treatment
Data Source	
The ORD includes enrollment, pharmacy, and medical claims data from a large U.S. health plan affiliated with Optum to identify eligible adult participants. The individuals covered by this health plan are geographically diverse across the US.

Data Analysis Methods	
Study endpoints and all other study variables will be analyzed descriptively. Numbers and percents will be provided for dichotomous and polychotomous variables. Means, medians, and standard deviations will be provided for continuous variables. Means and standard deviations will be provided for cost and utilization measures.
 
Primary Endpoints
 
Patient-reported symptom burden. Scores will be presented from validated instruments measuring dyspnea (mMRC) and condition-related burden of illness (CAT). Mean total, summary, and/or domain scores and standard deviations will be presented for each scale/item). Results will be presented for the overall study sample and will compare self-reported FLUT/SAL to UMEC/VI treatment cohorts. To address the objective of comparing symptom burden of patients by treatment cohort (FLUT/SAL as compared to UMEC/VI), inverse probability of treatment weighting (IPTW) will be applied to reduce confounding on observed clinical, demographic, and sociodemographic characteristics.
 
Proportion of patients reporting COPD symptoms while treated with FLUT/SAL or UMEC/VI. The proportion of patients who report COPD symptoms will be calculated as the number of COPD patients who report COPD symptoms as measured by the CAT, divided by the total number of respondents. Results will be presented for the overall study sample and by treatment cohort (FLUT/SAL or UMEC/VI).
 
Secondary Endpoints
 
Baseline health care resource utilization and costs. All-cause and COPD-related health care costs will be presented for the 12-month baseline period. Mean, median, and standard deviations will be presented for total costs and utilization and by each category of costs. Costs and counts will be presented overall and for the subset of patients utilizing the selected type of service. The proportion of patients receiving services for each type of service and the proportion of patients with non-zero costs for each type of cost will be calculated. Results will be presented for the overall study sample and by treatment cohort (FLUT/SAL or UMEC/VI).
 
Patient clinical characteristics. The proportion of patients with evidence of selected clinical characteristics will be presented. The top 20 claims-based comorbidities and 10 COPD-related comorbidities of interest will be identified. The percent of patients with each condition will be identified. Mean and standard deviation will be calculated for the Quan-Charlson comorbidity score. Results will be presented for the overall study sample and may be stratified by relevant subgroups for analysis (e.g., by symptom severity as measured by the mMRC and CAT, and by treatment).
 
Patient GOLD classification. The proportion of patients in each GOLD category of symptom burden and exacerbation (A, B, C, D) will be identified using the baseline


	
count of COPD exacerbations combined with CAT total score and mMRC score. GOLD categories are mutually exclusive. Results will be presented overall and by treatment cohort (FLUT/SAL or UMEC/VI).
 
Multivariable modeling of the primary objective will be conducted following review of descriptive and IPTW results. Each model will examine the relationship between symptom burden and treatment with FLUT/SAL or UMEC/VI. The dependent variable for the models will be CAT total score and mMRC score, respectively; covariates for the models will be based on clinical and analytic significance.

Sample Size and Power
	
The study sample is estimated to include 385 patients per cohort with evidence of COPD diagnosis and single-inhaler dual therapy treatment with FLUT/SAL or UMEC/VI. A sample size of n=385 per cohort is required to assess statistical significance with a 95% confidence interval at ± 0.05 with 80% power. A sampling frame of 2,700 patients is estimated to be used to reach the target evaluable sample size, n=770 patients (385/cohort). Based on patient counts and response rate estimates, it is anticipated that two waves of data collection will be needed to meet the target sample size.
 
This estimated study sample size is sufficient to detect proportional differences in PRO outcomes between two cohorts of patients (i.e., patients treated with FLUT/SAL or UMEC/VI who have severe symptoms as measured by a CAT total score ≥ 10 or an mMRC score ≥ 2); other stratifications tied to primary and secondary endpoints may be considered for statistically powered analyses as sample size allows.

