2.1 Primary

- The primary objective is to compare patient-reported COPD symptom burden among patients treated with UMEC/VI to those treated with FLUT/SAL.

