3.4.1 Primary Endpoint

- **Patient-reported symptom burden.** Scores will be presented from validated instruments measuring dyspnea (mMRC) and condition-related burden of illness (CAT). Mean total, summary, and/or domain scores and standard deviations will be presented for each scale/item (as described in Section 3.3.1.3). The proportion of patients with high and low symptom burden on both PRO measures will be calculated. Results will be presented for the overall study sample and by treatment cohort (FLUT/SAL or UMEC/VI).
- **Proportion of patients reporting COPD symptoms while treated with FLUT/SAL or UMEC/VI.** The proportion of patients who report COPD symptoms will be computed for survey respondents. Two calculations will be presented: the number of COPD patients who report COPD symptoms as measured by a CAT total score ≥ 10 , divided by the total number of respondents with a CAT total score; and the number of COPD patients with an mMRC score of 2-4, divided by the total number of respondents with an mMRC score. Results will be presented for the overall study sample and by treatment cohort.
- The mMRC and CAT instruments are included to correspond with current GOLD guidelines.

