3.5 Sample Size / Power Calculations

The sample size required for the study is based on several requirements. First, the study's primary outcome measures will be proportions (e.g., the proportion of patients experiencing symptoms who report low versus high symptom severity as measured by the mMRC and CAT total score). The estimated sample size is determined by the value and desired precision of the measured proportions.

Figure 6 displays the sample sizes required for various proportions, assuming a 95% confidence interval and a precision of ± 0.05 . Because the actual population proportions (e.g., the proportion of patients in each treatment cohort with mMRC scores ≥ 2 and the proportion of patients in each treatment cohort with CAT total scores ≥ 10) are unknown, the largest sample size indicated with that precision was selected. This largest value is for a proportion of 0.5 and assures a 95% confidence interval of ± 0.05 or

better for all proportions observed. Thus, a sample size of 385 completed patient surveys per treatment cohort was selected.

Figure 6 – Sample Sizes Required for Various Proportions

95% Confidence Interval	Proportion								
	0.9	0.8	0.7	0.6	0.5	0.4	0.3	0.2	0.1
±0.05	139	246	323	369	385	369	323	246	139

Since the proportion of patients experiencing symptoms will be determined from the survey and a variety of exclusion criteria can be applied only after data collection, a sampling frame of 2,700 patients is needed for an estimated evaluable sample size of 385 patients per treatment cohort. The sampling frame will be comprised of equal proportions per medication cohort (n=1,350 per cohort); however, proportional response rate by treatment cohort cannot be guaranteed. Based on the feasibility counts, Optum estimates that two waves of sample identification and survey data collection will be required to meet the target sample size. Sample identification for wave 2 will occur as soon as sufficient sample is available, which is estimated to be the month following wave 1 sample identification. The availability of the second wave will be assessed during protocol development.

Figure 7 – Estimated Final Evaluable Sample Size

Sampling frame per treatment cohort	n=1,350
Estimated response rate (30-35%)	405-470
Exclusion criteria applied following claims lag (2-5% ineligible)	8-24
Estimated final evaluable sample size per treatment cohort	385-446
Estimated total final evaluable sample size	770-892

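### The 385 per cohort comes from a single-proportion precision formula; the 80% power claim has no calculation behind it and no detectable between-cohort difference is stated

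*Combined protocol and SAP*

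**What the plan says.** The synopsis, under Sample Size and Power, states: "A sample size of n=385 per cohort is required to assess statistical significance with a 95% confidence interval", with a half-width of ± "0.05 with 80% power". Its next paragraph adds: "This estimated study sample size is sufficient to detect proportional differences in PRO outcomes between two cohorts of patients", with CAT ≥10 and mMRC ≥2 as the examples of severe symptoms.

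Section 3.5 gives the derivation. "The estimated sample size is determined by the value and desired precision of the measured proportions". Because the true proportions are unknown, "the largest sample size indicated with that precision was selected", which is the Figure 6 entry for a proportion of 0.5. Section 3.5 contains no power figure, no alternative rate and no between-cohort difference.

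Section 2.1 sets the aim: "The primary objective is to compare patient-reported COPD symptom burden among patients treated with UMEC/VI to those treated with FLUT/SAL". Section 3.6 states non-directional hypotheses 1A (CAT total score) and 1B (mMRC score) on the difference between cohorts, and says that the sample size and power work rests on that objective. Section 3.4.1 also lists per-cohort proportions as a primary endpoint, beginning with "the number of COPD patients who report COPD symptoms as measured by a CAT total score" of at least 10.

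**The concern.** A power figure means something only with a stated difference, test and error rate. Here 80% is attached to a confidence-interval half-width for one cohort's proportion, and a sentence about detecting differences between two cohorts follows. The detailed section that should support both statements supports neither.

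The primary comparison is therefore presented as powered when no one can say for what. The only number a reader is given is 5 points. It is easily taken as the study's sensitivity to a difference between treatments, but it describes each cohort separately. Someone appraising the design, or reading a non-significant comparison later, could credit the study with ruling out differences it was not sized to detect.

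**Working it through.** **Inputs from the documents.** 95% confidence, half-width 0.05, planning proportion 0.5 and 385 per cohort (Section 3.5 and Figure 6). The upper estimate is 446 per cohort (Figure 7, "Estimated final evaluable sample size per treatment cohort"). Allocation is 1:1 in the sampling frame.

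**Assumptions.** Two-sided 5%, taken from the 95% interval and the non-directional alternatives. No weighting. The proportions 0.7 and 0.8 are illustrative, since the protocol gives no expected rates.

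**1. Reproduce the plan's figure.** n = 1.96² × p(1−p) / 0.05².

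| p | Result | Rounded up | Figure 6 |
|---|---|---|---|
| 0.9 or 0.1 | 138.3 | 139 | 139 |
| 0.8 or 0.2 | 245.9 | 246 | 246 |
| 0.7 or 0.3 | 322.7 | 323 | 323 |
| 0.6 or 0.4 | 368.8 | 369 | 369 |
| 0.5 | 384.15 | 385 | 385 |

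Every entry reproduces. The formula uses one group and has no term for power or for an alternative, so 80% cannot come from it.

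**2. Precision of the between-cohort difference.** Half-width = 1.96 × √(2p(1−p)/n). At p = 0.5 and n = 385 this is 1.96 × √(0.5/385) = 0.0706. For a single cohort it is 1.96 × √(0.25/385) = 0.0499.

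**3. Difference detectable with 80% power.** This is the difference d at which a two-proportion test (pooled variance under the null) of p − d/2 against p + d/2 has power 0.80. A close approximation is 2.80 × √(2p(1−p)/n); at p = 0.5 and n = 385 that is 2.80 × √(0.5/385) = 0.101.

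| Centre p | Half-width, n=385 | Detectable, n=385 | Half-width, n=446 | Detectable, n=446 |
|---|---|---|---|---|
| 0.5 | 7.1 points | 10.1 points | 6.6 points | 9.4 points |
| 0.7 | 6.5 | 9.2 | 6.0 | 8.6 |
| 0.8 | 5.7 | 8.1 | 5.25 | 7.5 |

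For mean scores the detectable standardised difference is 2.80 × √(2/n): 0.20 SD at 385 and 0.19 SD at 446. This applies to mean CAT and mean mMRC alike.

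**4. Could the 0.05 be meant as the difference to detect?** The protocol does not say so, and at its own planning proportion 80% would not hold.

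- Between cohorts, 0.475 against 0.525: power is 28% at 385 and 32% at 446. About 1,569 per cohort would be needed for 80%.
- One cohort against a fixed 0.5, true value 0.55: power is 50% at 385, because the half-width equals the difference.
- At more extreme rates, power for 5 points at 385 rises to 33% centred on 0.7, 41% centred on 0.8, 75% for 0.90 against 0.95 (81% at 446) and 86% for 0.92 against 0.97. The protocol assumes none of these rates.

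**The case against.** The strongest reply is that 385 is a sound number with an openly stated basis. Per-cohort proportions are a primary endpoint, Section 3.5 says plainly that it sizes for precision, and its arithmetic is right. The claim of sufficiency is unsupported rather than shown false: 0.50 against 0.60 has 79.8% power at 385. Section 4.3 also mentions a 5-point CAT difference between stable and exacerbating patients. With a detectable difference of 0.202 SD, the SD would have to exceed 5/0.202 = 24.8 for that benchmark to be missed unweighted, which a 0–40 scale does not allow. Finally, what a completed comparison excludes is read from its confidence interval, not from planned power.

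Most of this stands. It supports keeping 385 and limits the point to what the plan claims. It does not supply a derivation for the 80% or name the difference it refers to. The protocol never adopts 10 points, 0.20 SD or the 5-point CAT figure as a between-cohort target. That the size happens to suit a 10-point difference is a reason to say so in the plan.

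**Conclusion.** The concern holds. The 385 is a correct one-sample precision figure. The statements that it carries 80% power and suffices to detect between-cohort differences have no calculation behind them, and no detectable difference is given. The documents do not show that the study is too small.

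At the planning proportion of 0.5, 80% power corresponds to a difference of about 10 points, twice the only figure the reader is given. This assumes a two-sided 5% test, equal cohorts and no weighting. Two features of the plan could make the detectable difference larger:

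- **IPTW (Section 4.4).** The documents give no effective sample size. If it were 80–100% of nominal (an assumption), the detectable difference at 0.5 would be 11.3 to 10.1 points, before any gain from the covariate-adjusted models in Section 4.5.
- **Two hypotheses, 1A and 1B.** No division of the error rate is stated. At 2.5% each, the detectable difference near 0.5 would be about 11.1 points.

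**What to change.** Keep 385 per cohort. In the synopsis, delete the 80% power phrase from the precision sentence and replace the sentence on detecting differences with, for example:

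> With 385 per cohort, each cohort's proportion is estimated to within ±5 points and the between-cohort difference to within about ±7 points at a proportion of 0.5. The unweighted comparison has 80% power (two-sided 5%) for a difference of about 10 points at 0.5, 9 at 0.7 and 8 at 0.8 (illustrative proportions), or 0.20 SD in mean CAT or mMRC score. Weighting may reduce the effective sample size and so increase these differences.

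Put the same figures in Section 3.5, with any allowance for weighting given as an explicit assumption. Reword Section 3.6 to say that the size was set for per-cohort precision and that the resulting detectable differences are in Section 3.5.

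The cost is wording in three places: no additional patients and no change to any analysis. The figure presented to readers becomes less favourable.

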PS	Propensity score
RRB	Research Review Board
SAE	Serious Adverse Event
SAL	Salmeterol
SAP	Statistical Analysis Plan
T2DM	Type 2 diabetes mellitus
UMECA	Umeclidinium
VI	Vilanterol

1 INTRODUCTION/BACKGROUND

Chronic obstructive pulmonary disease (COPD) is a prevalent respiratory condition characterized by a gradual loss of lung function and progressive airflow limitation that is not fully reversible.¹ COPD includes chronic bronchitis, chronic obstructive bronchitis, emphysema, and combinations of these conditions and is characterized by airflow obstruction that progressively worsens with time, leading to dyspnea, coughing, wheezing, sputum production, and/or exercise intolerance.²

COPD is estimated to affect 24 million people in the U.S.³ and is the third-leading cause of death in the U.S.⁴ Among the top six causes of death, COPD is the only one that continues to increase in incidence.⁵ The prevalence of COPD is rising with the increasing proportion of the population over the age of 65, and the burden of COPD is projected to rise considerably over the next 15-20 years, driven largely by increasing prevalence and population demographics. Recent reports indicate that COPD accounts for 1.5 million emergency department (ED) visits and 636,000 inpatient hospitalizations (IP) annually in the United States.^{6,7} The quality of life and economic impact of COPD are substantial; treatments that can improve management of COPD and reduce use of healthcare services can both improve patient quality of life and reduce health care expenditures.

Studies of COPD patients have demonstrated that those with higher adherence to their prescribed treatment regimens experienced fewer hospitalizations and lower medical costs than patients who exhibited lower adherence behaviors.⁸ Ease and frequency of use are important considerations in disease management. Products that are easier for patients to use consistently may improve treatment adherence, thereby resulting in improved symptom management. By helping to better manage symptoms, improved adherence may also improve health-related quality of life, exercise tolerance, and other pro-health behaviors, thereby helping to mitigate disease progression.

regular treatment with one or more long-acting bronchodilators as the disease progresses.¹¹ Inhaled long-acting bronchodilators, which include long-acting anticholinergics and long-acting β -agonists (LABAs), improve the airflow obstruction that characterizes COPD.

Dual therapies combined into single-inhaler, fixed dose delivery systems are important to examine in the context of simplifying treatment, improving adherence and quality of life, and managing disease progression. Umeclidinium/vilanterol (UMEC/VI 62.5/25 mcg; Anoro® Ellipta®) is a once-daily single inhaler dual LAMA/LABA therapy that was FDA-approved for the treatment of COPD in December 2013. Fluticasone/salmeterol (FLUT/SAL 250/50 mcg; Advair® Diskus®) is a twice-daily single inhaler dual therapy ICS/LABA treatment approved by the FDA for COPD treatment in November 2003. To better understand variation in burden of illness associated with these treatments, this study will provide evidence about associations between symptoms, clinical, economic, and sociodemographic characteristics, and GOLD classification for patients treated with UMEC/VI as compared to those treated with FLUT/SAL. Results of the study may be of interest to health care providers treating COPD patients and to third party payers.

The overall purpose of this study is to describe patient-reported symptom severity and claims-based healthcare utilization and costs among COPD patients treated with UMEC/VI or FLUT/SAL single-inhaler dual therapies in a real-world setting.

